6.3.16 HCV Therapy Dispensed/First Dose Observed

The entire quantity of study-provided drug (84 tablets) will be dispensed at the entry visit (week 0). Study staff will observe the first dose taken by the participant before he/she leaves the site and record this observation on an eCRF. Refer to section 5.0 for details on study product dispensation.

6.3.17 Adherence Education and Counseling

Adherence education and counseling will be conducted for all participants prior to entry. Adherence education and counseling is not recorded on the eCRF.

See the A5360 MOPS for further details.

6.3.18 Pregnancy Prevention Counseling

Pregnancy prevention counseling will be conducted for all participants at screening and entry. Pregnancy prevention counseling is not recorded on the eCRF.

6.3.19 Cirrhosis Counseling

All compensated cirrhotics will be counseled on secondary prevention and long-term surveillance of liver disease according to the SOE. Cirrhosis counseling is not recorded on the eCRF.

See the A5360 MOPS for further details.

6.3.20 HCV Risk-reduction Counseling

HCV risk-reduction counseling will be administered to all participants, per the SOE. See the A5360 MOPS for further details.

6.3.21 Locator Information

At study entry, all participants will be asked to list their primary mode of contact (e.g., telephone, email, text, or social media) and their secondary mode of contact. The site will capture these options for mode of contact (but will not record any participant locator this information on any eCRF), and use them to contact study participants without requiring them to come in to the clinic. Sites will also capture information on another person that the site can contact if the participant cannot be reached (e.g., spouse, friend, neighbor, etc.); information on the secondary contact will not be recorded on any eCRF.

6.3.22 Remote Contact with Participants Outside of Planned Clinic Visits

When contacting participants remotely, sites will have the flexibility to make adjustments to the mode of contact utilized at their discretion and at the participant's convenience – the only mode that will not be allowed is to schedule clinic visits in place of the remote contact. Sites will also be able to use different modes to contact different participants. Additionally, how the participant was contacted (i.e., mode of contact) will be collected on the eCRF.

Data that will be captured from the participant during the week 4 remote contact is whether the participant is taking study medication (i.e., adherence), in the prior 4 weeks. All participants will receive an individually tailored message, based on their adherence, which will be read or written to them in order to promote and/or encourage adherence through the end of treatment. The message will highlight the benefit of treatment for HCV and the importance of adherence and will be tailored to each participant's response as to how well he/she is adhering to the HCV treatment regimen. Additionally, at both weeks 4 and 22, locator information will be updated (if anything has changed) and participants will be reminded to return for their SVR evaluation visit. Sites will be allowed to contact and collect participant's responses on adherence and to update his/her locator information using any of the options listed above, namely phone call, text message, email, or social media (e.g., WhatsApp, Facebook Messenger, Twitter, etc.; for a complete list, please refer to the MOPS). If the participant comes in for the week 24 visit prior to the completion of the week 22 remote call, or if the participant has completed the discontinuation visit, then the week 22 remote call is not needed.

The remote contact is not designed to assess concomitant medications or AEs. At the end of each remote contact, participants will be reminded that the information that they shared will not be communicated to the study team and that if they have concerns about symptoms or study questions they should contact the site via the telephone number provided by the site. This information should be reported in a medical record then reviewed and entered into an eCRF at the week 24/SVR evaluation visit.

Since it is common for participants to lose mobile phones or change service providers in a 6-month period, it is critical to ensure that locator information is kept up-to-date to ascertain SVR status. Locator information will be maintained securely by sites and specific locator information will not be recorded onto an eCRF. However, the parts of the locator information that were updated and the mode of contact used to update this information will be recorded on an eCRF.

Participants will be provided with a telephone number to contact the study staff if they are experiencing any side effects or have any safety concerns. If the study staff contacted determines that the issue cannot be resolved over the phone, an unplanned study visit will be scheduled, as described in section 6.2.6. If participant calls but does not come in for an unplanned study visit, details related

to the call should be reported in the participant medical record and reviewed at week 24/SVR evaluation visit and entered into the eCRF.

See the A5360 MOPS for further details, including a script to be used by site staff when contacting participants.

7.0 ADVERSE EVENTS AND STUDY MONITORING

7.1 Definition of Adverse Events

An AE is any unfavorable and unintended sign (including an abnormal laboratory finding), symptom, or diagnosis that occurs in a study participant during the conduct of the study REGARDLESS of the attribution (i.e., relationship of event to medical treatment/study product/device or procedure/intervention). This includes any occurrence that is new in onset or aggravated in severity or frequency from the baseline condition.

7.2 Adverse Event Collection Requirements for This Protocol

Post-entry, all AEs must be recorded on the eCRFs if any of the following criteria have been met.

- All grade ≥ 3 AEs
- All AEs that led to a change in study treatment/intervention regardless of grade
- All AEs meeting SAE definition or EAE reporting requirement

NOTE: SAEs or events meeting EAE reporting requirements should also be entered into the DAIDS Adverse Experience Reporting System (DAERS), an internet-based reporting system.

NOTE: At week 24/SVR evaluation visit, information on any AEs participants may have experienced during the prior 24 weeks (particularly while on study medication) will be collected unless this information was already obtained during an unplanned study visit.

All AEs that are reported must have their severity graded. To grade AEs, sites must refer to the Division of AIDS Table for Grading the Severity of Adult and Pediatric Adverse Events (DAIDS AE Grading Table), corrected Version 2.1, July 2017, which can be found on the DAIDS RSC website at <http://rsc.tech-res.com/clinical-research-sites/safety-reporting/daids-grading-tables>.

Serious Adverse Events (SAEs)

A SAE is defined as any untoward medical occurrence that:

- Results in death
- Is life-threatening
- Requires inpatient hospitalization or prolongation of existing hospitalization
- Results in persistent or significant disability/incapacity
- Is a congenital anomaly/birth defect
- Is an important medical event that may not be immediately life-threatening or

result in death or hospitalization but may jeopardize the patient or may require intervention to prevent one of the other outcomes listed in the definition above).

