6.2.4 Post-Entry Evaluations

Given the design of the MINMON strategy, there will be no on-treatment or EOT evaluations. See section 6.3.22 for post-entry site contact with participants via remote mechanism.

Post-Treatment Evaluations

Step 1: Following treatment completion at week 12, participants will undergo evaluations as outlined in the SOE 6.1-1.

NOTE: If the participant comes in for the week 24 visit during the -14 days window (i.e., week 22), then the week 22 remote call is not needed.

Week 24/SVR Evaluation Visit

The week 24 visit (visit window: week 22-28) is ideally the visit where SVR should be assessed for all participants, and subsequently they will be registered to Step 2. However, if a participant misses the visit window (>week 28), the week 24 visit will be considered a missed visit and he/she will need to be scheduled for an SVR visit prior to being registered to Step 2 of the study. The SVR visit can

take place at any time point after week 28 and up to week 72 and is mandatory for the participant to be registered to Step 2.

NOTE: Participants will be reminded of the week 24/SVR visit during the remote contact (at weeks 4 and 22), and participants only need to complete either the week 24 OR the SVR evaluation visit; they will not be required to complete both. If a participant completes week 24, his/her next visit will be at week 48 on Step 2. If a participant misses the week 24 visit and returns to the clinic for the SVR visit either at week 48 or 72, then only the SVR evaluations will be performed at that visit time point. Evaluations for weeks 48 or 72 will be performed at the next scheduled study visit. However, if a participant completes their SVR visit at week 72, this visit will be the participants' last study visit and they will not enter Step 2.

Step 2 Registration

Following completion of the SVR evaluation on Step 1 (Week 24 OR SVR visit), participants will be registered to Step 2 on that same day. Participants will undergo evaluations as outlined in the SOE 6.1-2, within the ±28-days visit window, as appropriate for the visit.

NOTE: Participants who register into Step 2 within the week 48 visit window will complete the week 48 and 72 visits. If a participant registers into Step 2 after the week 48 visit window, site staff should have the participant return to the clinic to complete week 72 (final study visit).

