6.3.10 Clinical Assessments

Complete Physical Exam

A complete physical examination must be performed at screening and is to include at a minimum an examination of the skin, head, mouth, and neck; auscultation of the chest; cardiac exam; abdominal exam; and examination of the lower extremities for edema. The complete physical exam will also include signs and symptoms, diagnoses, and vital signs (height, weight, temperature, pulse, respiration rate, and blood pressure).

Targeted Physical Exam

A targeted physical examination should be performed at entry, week 24/SVR evaluation visit and weeks 48 and 72, and should include vital signs (weight, temperature, pulse, respiration rate, and blood pressure), and is to be driven by any previously identified or new AE/targeted condition (as described in below bullets), that the participant has experienced within 14 days prior to study entry/since the last visit or at this visit.

Post entry, record the following targeted events regardless of grade:

- Uterine pregnancy
- AIDS-defining conditions (refer to the CDC HIV Classification and the WHO Staging System for HIV Infection and Disease)
- Tuberculosis
- Chronic HBV
- Ascites
- Hepatic Encephalopathy

Refer to section 7.2 for AE collection requirements.

Height

Height (in cm) will be collected once at study screening.

Weight

Weight (in kg) will be collected at study screening, entry, week 24/SVR evaluation visit, and weeks 48 and 72.

Concomitant Medications

At entry and at the week 24/SVR evaluation visit, new and discontinued concomitant medications should be recorded on the eCRFs. See section 5.4 for concomitant medications.

Study Treatment (Intervention) Modifications

When the participant takes the last tablet of each bottle of SOF/VEL, they will be instructed to contact the site to report the treatment stop date. This information self-reported by the participant should be captured on the eCRF when reported outside of and during the week 24/SVR evaluation visit. See A5360 MOPS for additional details.

At the week 24/SVR evaluation visit, record all study drug modifications, including participant-initiated modifications, inadvertent and deliberate interruptions of more than 7 days. Record permanent discontinuation of study treatment (see section 6.2.7).

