8.0 CLINICAL MANAGEMENT ISSUES

8.1 Toxicity

Criteria for participant management, dose interruptions, dose adjustments and discontinuation, or changes in treatment will be described only for toxicities attributable to study drugs (SOF/VEL). The grading system for drug toxicities is located in the DAIDS AE Grading Table (see section 7.2).

NOTE: The team must be notified via e-mail within 72 hours regarding toxicities that result in a change in study regimen ([contact]).

It is possible that some participants will experience transient or prolonged AEs during the study. However, it is important to note that, in this trial, there are no scheduled on-treatment visits and hence, participants must call the site and schedule unplanned study visits in order for AEs to be identified. AE-related unplanned study visits will be handled as listed below. However, at week 24, information on any AEs participants may have experienced during the prior 24 weeks, particularly while on study medication, will be collected.

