5.1.3 Analysis Sets

Enrolled participants who do not start study medication will be excluded from all analyses. Note that per protocol instructions, the first dose of study medication is to be observed in the study clinic during the entry evaluation visit.

Full analysis sample (= Efficacy analysis sample at final analysis): Participants who started study medication. For the efficacy analysis sample for interim reviews, refer to section: 4.1.1 Primary Efficacy Outcome Measure. At interim analyses, the efficacy analysis sample will differ from the full analysis sample as follows: participants missing HCV RNAs for SVR evaluation will not be counted as SVR non-responders unless they enrolled more than 76 weeks prior to dataset finalization. Thus, the efficacy analysis sample at interim reviews will be based on observed HCV RNAs in the SVR evaluation window plus participants who both left the study without a result for SVR evaluation and who enrolled more than 76 weeks ago (and thus can no longer be evaluated for SVR on study).

Safety analysis sample: Participants who started study medication and who were evaluated for AEs for the time period after first dose of study treatment through up to 24 week later. This criterion will be met for any participant having an unscheduled visit prior to week24/SVR evaluation, or any participant having a week 24 or SVR evaluation visit. At interim analysis, due to no planned study clinic visits prior to study week 24, this analysis sample include all participants who started treatment, and only exclude those who were both known lost to all follow-up and without any follow-up for AEs. This sample will be split into subgroups defined by those having week 24/SVR evaluation visit versus not.

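### The 24-week AE look-back at the SVR visit reaches study entry only for visits by week 24, yet the SAP counts an SVR visit at any date as AE evaluation from first dose

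*Protocol*

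**What the plan says.** Protocol 7.2 fixes the AE inquiry at the week 24/SVR visit as follows: "information on any AEs participants may have experienced during the prior 24 weeks (particularly while on study medication) will be collected". What an unplanned visit has already obtained is excepted. Protocol 8.1 gives the same look-back but ties it to the scheduled visit: "at week 24, information on any AEs participants may have experienced during the prior 24 weeks, particularly while on study medication, will be collected".

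The visit itself is not tied to week 24. Its window runs from week 22 to week 28. If that is missed, Protocol 6.2.4 lets the SVR visit "take place at any time point after week 28 and up to week 72", and Protocol 10.1 allows SVR evaluation up to 76 weeks after entry.

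No earlier planned contact collects AEs. There are no on-treatment visits, and Protocol 6.3.22 states that the remote contacts are not meant to assess AEs.

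Other passages use a different reference period:
- Protocol 7.2 opens with a general rule that has no look-back limit: "Post-entry, all AEs must be recorded on the eCRFs if any of the following criteria have been met".
- Protocol 6.3.10 frames the targeted examination at this visit around conditions "experienced within 14 days prior to study entry/since the last visit or at this visit".
- Protocol 7.3.4 runs expedited reporting from week 0 to the week 24/SVR evaluation.

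SAP 5.1.3 requires members of the safety sample to have been evaluated for AEs from first dose for up to about 24 weeks. It then treats this as met by an unscheduled visit before the SVR evaluation, "or any participant having a week 24 or SVR evaluation visit", with no condition on the visit date.

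**The concern.** The look-back counts backwards from the visit, while the safety outcomes count forwards from study entry (Protocol 10.2.1) or first dose (SAP 4.1.2). The two agree only when the visit is on time. For a late attender, a site that follows the 24-week wording exactly asks about a period that misses some or all of treatment. The SAP nevertheless places that participant in the denominator as fully evaluated.

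The SAE percentage is a primary outcome and the other-AE percentage a secondary one. Any weeks not asked about count as event-free, so an error from this source lowers both percentages, which is the reassuring direction. Because AEs otherwise surface only if the participant calls or comes in, little else in the design would recover a missed event.

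**Working it through.** **Inputs.** Look-back: 24 weeks before the visit (Protocol 7.2, 8.1). Treatment: weeks 0–12 (Protocol 5.1.2). Safety window: weeks 0–24 in Protocol 10.2.1, weeks 0–28 in SAP 4.1.2. Permitted SVR visit: week 22 to week 72 or 76 (Protocol 6.2.4, 10.1). Sample size: 400. The plan states no figure that depends on the look-back, so there is none to reproduce for that step.

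**Step 1: coverage on a literal reading.** For a visit at week V, the interval asked about is [max(0, V − 24), V]. Its overlap with each period is:

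| Visit week V | Interval asked about | Treatment 0–12 | Protocol window 0–24 | SAP window 0–28 |
|---|---|---|---|---|
| 24 | 0–24 | 12/12 | 24/24 | 24/28 |
| 26 | 2–26 | 10/12 | 22/24 | 24/28 |
| 28 | 4–28 | 8/12 | 20/24 | 24/28 |
| 32 | 8–32 | 4/12 | 16/24 | 20/28 |
| 36 | 12–36 | 0/12 | 12/24 | 16/28 |
| 48 | 24–48 | 0/12 | 0/24 | 4/28 |
| 52 or later | starts at 28 or later | 0/12 | 0/24 | 0/28 |

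The loss begins inside the permitted week 22–28 window, is partial between weeks 24 and 36, and is complete for treatment from week 36.

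**Step 2: coverage if the inquiry runs from entry.** The interval becomes [0, V]. Coverage is 12/12 treatment weeks and 24/24 protocol weeks for any V ≥ 24, and 28/28 SAP weeks for any V ≥ 28.

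**Step 3: possible size.** The documents do not say how many participants will be seen late. Let L be the number seen at week 48 or later and s the true SAE risk. Take the worst case, in which every SAE in these participants is missed. The reported percentage is then s × (400 − L)/400.

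- s = 5%, L = 20: 5.0% × 380/400 = 4.75% (1 of 20 SAE participants missed).
- s = 5%, L = 40: 5.0% × 360/400 = 4.5% (2 of 20 missed).
- s = 1%, L = 4 to 40: 0.99% to 0.90%.

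Over L = 4 to 40, the relative loss is L/400, which is 1% to 10% whatever s is.

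L and s are assumptions. The value 5% is borrowed from Protocol 10.5.1, where it is the upper confidence bound from the cited HIV co-infection trial, not an expected rate. On L, Protocol 2.2 says that roughly 20% of US patients who complete treatment do not return promptly for SVR assessment. Applied to the US cap of 132, that is 0.20 × 132 ≈ 26. But promptness is not defined there, and this trial adds an attendance incentive, so the figure gives only a sense of scale.

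**Step 4: comparison with sampling error.** The Wilson 95% interval for 20/400 is 3.3% to 7.6%, a width of 4.3 points. This mirrors the 95% row of Protocol Table 10.4-3 (92.4% to 96.7%), which reproduces. The worst-case shift of 0.25 to 0.5 points is small beside it.

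**The case against.** A reader might infer that late attenders are not asked about the treatment period at all, and that the primary safety estimate is therefore biased. The documents do not support that.

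- The look-back sentence singles out the time on medication. A site could not follow that emphasis at week 36 or later if it stopped at 24 weeks. Since 8.1 ties the phrase to week 24, it reads naturally as shorthand for the time since entry at an on-time visit.
- The opening rule of 7.2 covers all qualifying post-entry AEs. Section 7.3.4 runs from week 0 to the SVR evaluation, however late, and 6.3.10 looks back to the previous visit, which is entry if no unplanned visit occurred.
- SAP 4.1.2 classifies events by when they occurred. It expects that a week 23 event might surface only at week 48, which is longer than a 24-week recall.
- Protocol 6.3.22 has participants' calls documented, then reviewed and entered at the SVR visit.
- The eCRF prompts and the MOPS, which may settle the matter, are not among the documents.

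This defeats the absolute claim. It does not remove the conflict. The opening rule of 7.2 and section 7.3.4 say which events must be recorded or expedited; they do not say what period participants are asked about. Section 6.3.10 sends sites back to 7.2 for AE collection, where the 24-week wording stands. And if the SAP relies on longer recall, the protocol sentence should say so. A link between late attendance and illness or early stopping is plausible, but the documents give no evidence for it.

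**Conclusion.** The point holds as an inconsistency within the protocol, and between protocol and SAP, that permits under-ascertainment in participants seen late. It does not show that such participants go unasked or that the estimate is biased. The coverage figures are exact on a literal reading of 7.2.

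The effect on the SAE percentage cannot be computed from the documents. With 20 to 40 of 400 seen at week 48 or later, a 5% risk and all their SAEs missed, it is 0.25 to 0.5 points. That is close to an upper limit for those inputs, since other text may lead sites to ask back to entry and, under the SAP window, a visit between weeks 48 and 52 still reaches part of weeks 24–28. Partial losses for visits between weeks 24 and 48 are not included. The change is still worth making because it is nearly free and protects a primary outcome from an error in the reassuring direction.

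**What to change.** In Protocol 7.2 and 8.1, replace the 24-week look-back with *since study entry*, whatever the week of the visit, and align the eCRF and MOPS prompts.

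Leave the membership rule of the safety sample in SAP 5.1.3 as it is. An added condition would be redundant once the protocol is reworded. Without the rewording, it could drop the late attenders, replacing possible under-ascertainment with selection. Instead, show the SAE and other-AE percentages separately for participants whose SVR visit fell after week 28. No new rule on onset dates is needed, because the SAP already classifies events by when they occurred.

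The cost is one phrase in two protocol sections, a check of the site prompts and one extra table split, with no added visit or test. The drawback is a longer recall period for late attenders, whose reports of early events will be less reliable; the separate display lets readers judge that.

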7.3 Expedited Adverse Event (EAE) Reporting to DAIDS

7.3.1 Expedited Reporting of Adverse Events to DAIDS

Requirements, definitions and methods for expedited reporting of Adverse Events (AEs) are outlined in Version 2.0 of the DAIDS EAE Manual, which is available on the RSC website at <http://rsc.tech-res.com/clinical-research-sites/safety-reporting/manual>.

DAERS must be used for EAE reporting to DAIDS. In the event of system outages or technical difficulties, EAEs may be submitted using the DAIDS EAE Form. This form is available on the DAIDS RSC website at <http://rsc.tech-res.com/clinical-research-sites/safety-reporting/daids/paper-eae-reporting>.

For questions about DAERS, please contact NIAID CRMS Support at [contact]. Please note that site queries may also be sent from within the DAERS application itself.

For questions about expedited reporting, please contact the DAIDS RSC Safety Office at [\([contact]\)](mailto:([contact])).

